8.3.9 Withdrawal of Participants

8.3.9.1 Discontinuation of Study Medication

Participants MUST discontinue investigational product (IP) (and non-investigational product [non-IP] at the discretion of the investigator) for any of the following reasons.

- Participant's request to stop study medication. Participants who request to discontinue study medication will be expected to complete an ET Visit and subsequent follow-up visits/procedures per the Schedule of Activities (e.g., Week 52/PTFU; Section 1). The only exception to this is when a participant specifically withdraws consent for any further contact with him/her or persons previously authorized by participant to provide this information. Participants' withdrawal of consent should be explained in detail in the medical records by the investigator as to whether the withdrawal is from further treatment with study medication only or also from study procedures and/or ET, Week 52/PTFU Visit, etc. (see [Section 8.3.9.2](#))
- Any clinical AE, laboratory abnormality or intercurrent illness, which, in the opinion of the investigator, indicates that continued participation in the study is not in the best interest of the participant
- The participant experiences a major bone fracture or is diagnosed with osteoporosis that requires treatment
- Abnormal liver tests as defined in [Section 8.5.3.1](#)
- On 2 consecutive visits (at least 2 weeks apart), a participant has an eGFR < 30 mL/min/1.73 m², according to the *Modification of Diet in Renal Disease Study* equation
- If there is a significant protocol violation. The violation should be discussed with the medical monitor prior to discontinuing study medication
- Loss of ability to freely provide consent through imprisonment or involuntary incarceration for treatment of either a psychiatric or physical (e.g., infectious disease)

illness (Note: Under specific circumstances, a participant who has been imprisoned may be permitted to continue as a participant. Strict conditions apply, and sponsor approval is required.)

- The participant becomes pregnant (study medication must be discontinued immediately)

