8.4.6 Dose Modification

8.4.6.1 Modification of Dose

No dose reductions or modifications are allowed. If a participant interrupts treatment due to an AE, study medication may be restarted after consultation with the medical monitor.

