8.4.6.2 Dose Interruption

If a participant has abnormal laboratory test result(s) and/or clinical AE(s) that, in the judgment of the investigator, could place the participant at risk, study medication administration should be interrupted, and the investigator should notify the medical monitor. Participants may receive further study medication when the AE or abnormal laboratory finding is resolved.

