- Participants with elevated Baseline aminotransferase values experience additional increases greater than $2\times$ the Baseline (with concomitant elevations of total bilirubin $> 2\times$ ULN) **AND** ALT and/or AST is > 200 U/L.

If the new elevations in aminotransferases persist and the participant is symptomatic, then the drug should be discontinued, and the participant should be evaluated for other causes of liver injury or disease. The medical monitor should be contacted within 48-72 hours.

If the participant is asymptomatic, the participant should be placed under “close observation”, defined as physical examination and laboratory evaluation 2-3 times per week.

If close observation is not possible, study medication should be discontinued. The frequency of retesting can decrease to once a week or less if abnormalities stabilize or the study medication has been discontinued and the participant is asymptomatic.

Discontinuation or Temporary Interruption of Study Medication

In addition to the reasons for discontinuation described above, study medication should be discontinued or temporarily interrupted if either of the 2 following scenarios occur:

1) Aminotransferases (ALT and/or AST) $> 2\times$ Baseline and aminotransferases $> 3\times$ ULN **and** either:

- i. the increase is accompanied by a concomitant increase in total bilirubin to $> 2\times$ Baseline **OR** the INR concomitantly increases by > 0.2 ;

OR

- ii. there are concomitant signs and symptoms of new-onset fatigue, nausea, vomiting, right upper quadrant pain or tenderness, fever, rash, and/or eosinophilia ($> 5\%$).

2) Total bilirubin increases to $> 2\times$ ULN **AND**:

- i. there are concomitant signs and symptoms of new-onset fatigue, nausea, vomiting, right upper quadrant pain or tenderness, fever, rash, and/or eosinophilia ($> 5\%$).

If the above rule is met, a potential DILI work up for competing etiologies (e.g., alcohol use, viral hepatitis, biliary obstruction, autoimmune liver disease) must be performed, and a complete liver profile including INR must be repeated within 48-72 hours. **The medical monitor should be contacted within 48-72 hours.** Study medication can be restarted only if an alternative etiology is definitively identified and liver tests (aminotransferases, total bilirubin and/or INR) have returned to Baseline.

Other Safety Considerations

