Is an important medical event (defined as a medical event(s) that may not be immediately life-threatening or result in death or hospitalization but, based upon appropriate medical and scientific judgment, may jeopardize the participant or may require intervention [e.g., medical, surgical] to prevent one of the other serious outcomes listed in the definition above); examples of such events include, but are not limited to, intensive treatment in an emergency room or at home for allergic bronchospasm; blood dyscrasias or convulsions that do not result in hospitalization.
Wherever possible, timely confirmation of initial liver-related laboratory abnormalities should occur prior to the reporting of a potential DILI event. All occurrences of potential DILIs, meeting the defined criteria, must be reported as SAEs.
Potential DILI is defined as: 
• ALT or AST $> 3 \times$ ULN AND• Total bilirubin $> 2 \times$ ULN, without initial findings of cholestasis (elevated serum alkaline phosphatase) AND• No other immediately apparent possible causes of ALT or AST elevation and hyperbilirubinemia, including, but not limited to, viral hepatitis, pre-existing chronic or acute liver disease, or the administration of other drug(s) known to be hepatotoxic

Suspected transmission of an infectious agent via the study medication is an SAE.

Although pregnancy, overdose, cancer, and potential DILI are not always serious by regulatory definition, these events must be handled as SAEs.

Evaluating AEs and SAEs

Assessment of Intensity
The intensity of AEs is determined by a physician and will use the following level:

• Mild: An event that is easily tolerated by the participant, causing minimal discomfort, and not interfering with everyday activities• Moderate: An event that causes sufficient discomfort and interferes with normal everyday activities

- Severe: An event that prevents normal everyday activities. An AE that is assessed as severe should not be confused with an SAE. Severe is a category utilized for rating the intensity of an even; and both AEs and SAEs can be assessed as severe.

Assessment of Causality

The causal relationship to study medication is determined by a physician and should be used to assess all AEs. The causal relationship can be one of the following:

Related: There is a reasonable causal relationship between study medication administration and the AE.

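### Section 8.5.3.1 sets no numeric interruption, mandatory work-up or etiology-based restart limit for an asymptomatic potential-DILI case whose raised baseline ALT/AST has not doubled

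*Protocol*

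**What the plan says.** Appendix 8 defines potential DILI by three conditions together: ALT or AST > 3× ULN; total bilirubin > 2× ULN without initial cholestasis; and "No other immediately apparent possible causes of ALT or AST elevation and hyperbilirubinemia", with pre-existing liver disease listed among such causes. It adds: "All occurrences of potential DILIs, meeting the defined criteria, must be reported as SAEs".

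Section 8.5.3.1 sets the dosing response separately: "study medication should be discontinued or temporarily interrupted if either of the 2 following scenarios occur".

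- Scenario 1: ALT and/or AST > 2× Baseline and > 3× ULN, plus bilirubin > 2× Baseline, or an INR rise > 0.2, or a listed sign, symptom or eosinophilia > 5%.
- Scenario 2: bilirubin > 2× ULN plus one of the same signs, symptoms or eosinophilia > 5%.

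Baseline here is the mean of the Screening and Day 1 results. If a scenario is met, a work-up for competing causes is mandatory, a full liver profile with INR is repeated within 48–72 h, and the medical monitor is contacted in the same period. "Study medication can be restarted only if an alternative etiology is definitively identified" and the liver tests are back to Baseline.

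An earlier step in 8.5.3.1 asks for repeat tests within 48–72 h. One trigger is a normal baseline (ALT and/or AST) rising above 3× ULN. The other is that "Participants with elevated Baseline aminotransferase values experience additional increases greater than" 2× Baseline, with bilirubin > 2× ULN and ALT and/or AST > 200 U/L. Asymptomatic participants then go to close observation two to three times weekly, with a stop if that is not possible.

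Elsewhere, 8.3.9.1 requires discontinuation for abnormal liver tests but refers back to 8.5.3.1 to define them. It also requires discontinuation when the investigator considers that "continued participation in the study is not in the best interest of the participant". Under 8.4.6.2, if the investigator finds that a result "could place the participant at risk, study medication administration should be interrupted, and the investigator should notify the medical monitor"; dosing may resume once the finding resolves. Under 8.4.6.1, after an AE interruption "study medication may be restarted after consultation with the medical monitor".

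**The concern.** The protocol recognizes a potential-DILI case by multiples of ULN but acts on dosing mainly by multiples of Baseline. SAP Section 4.3.5 uses the same absolute pair (AST or ALT > 3× ULN with bilirubin > 2× ULN) as a potential hepatotoxicity category. The trial would therefore report and tabulate some cases that its own stop rule does not reach.

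Restart is the sharpest consequence. A careful investigator who interrupts under 8.4.6.2 may resume dosing once the abnormality resolves, after medical monitor consultation under 8.4.6.1, without any alternative cause having been found. For scenarios 1 and 2 the protocol forbids exactly that.

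**Working it through.** The plan states no figure on this point, so there is none to reproduce. The check applies the rules to numbers.

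**Inputs.** Potential-DILI limits from Appendix 8; scenarios and repeat-test triggers from 8.5.3.1; entry limits from 8.3.2, criteria 5b–5d (ALT and AST up to 5× ULN; bilirubin up to 1.5 mg/dL, with documented Gilbert's syndrome exempt). Bilirubin ULN and ALT ULN are not given and are assumed where needed.

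**Main gap.** It requires 3× ULN < enzyme ≤ 2× Baseline. That range is non-empty only if 2 × Baseline > 3 × ULN, so Baseline > 1.5× ULN in that enzyme. Counting only values above baseline, the range is max(3× ULN, Baseline) to 2× Baseline:

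| Baseline (× ULN) | Range not reached (× ULN) |
|---|---|
| 1.5 or lower | none |
| 1.6 | 3–3.2 |
| 2 | 3–4 |
| 3 | 3–6 |
| 5 (entry limit) | 5–10 |

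These ranges use the laboratory limits only. Appendix 8 also requires no other apparent cause, so they are upper bounds.

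**Worked case.** All values are × ULN; no listed sign, symptom or eosinophilia > 5%; no cholestasis; NASH not considered an apparent cause.

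| | Baseline | On treatment | Ratio to Baseline |
|---|---|---|---|
| ALT | 2.0 | 3.9 | 3.9/2.0 = 1.95 |
| AST | 1.2 | 2.3 | 2.3/1.2 = 1.92 |
| Bilirubin | 0.6 | 2.5 | 2.5/0.6 = 4.17 |

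- Appendix 8: 3.9 > 3 and 2.5 > 2, so it is met.
- Scenario 1: neither enzyme exceeds 2× Baseline, so it fails. An INR rise > 0.2 does not rescue it, because INR counts only once the enzyme condition is met. Letting different enzymes satisfy the two enzyme conditions does not rescue it either.
- Scenario 2: no listed sign or symptom, so it fails.
- Repeat-test triggers: both baselines are above normal and neither enzyme has doubled, so neither fires.

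With ALT at 4.1× ULN instead (4.1/2.0 = 2.05× Baseline), scenario 1 is met without symptoms.

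**Grid check.** One aminotransferase was varied with bilirubin and an INR rise of 0 or 0.3, always asymptomatic. Of 34,944 combinations in the main gap, none met a stop scenario or a repeat-test trigger. These are grid points, not expected patients.

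**Smaller gap.** The enzyme has doubled, but bilirubin is > 2× ULN and not > 2× Baseline, with an INR rise of 0.2 or less. It needs baseline bilirubin above ULN. At a baseline of 1.5 mg/dL the range is 2.0–3.0 mg/dL for an assumed ULN of 1.0, 2.4–3.0 for 1.2, 2.6–3.0 for 1.3, and empty for 1.5. Of 4,488 such grid points, none met a stop scenario without an INR rise and all did with a rise of 0.3. Without the INR rise, a repeat-test trigger still fired in 3,894/4,488 = 87%, 4,268/4,488 = 95% and 4,444/4,488 = 99% for assumed ALT ULN of 30, 40 and 55 U/L.

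**No gap from these two conditions** when both enzyme baselines are at or below 1.5× ULN and baseline bilirubin is at or below ULN.

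**The case against.** The strongest reply is that the main gap largely closes itself. Appendix 8 excludes cases with another apparent cause and names pre-existing liver disease. Every participant has biopsy-confirmed NASH with stage 3 fibrosis, and the gap concerns those whose enzymes were already raised and have not doubled. NASH is the most natural explanation there, above all at the highest baselines. This stands: it limits frequency and makes the numeric ranges upper bounds. It does not cover the case where the investigator finds that NASH is not an apparent cause of both the enzyme level and the bilirubin rise.

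Second, other controls remain. SAEs are reported within 24 hours and followed until resolution, stabilization or explanation (8.5.3.1 and Appendix 8). Prompt confirmation is asked for where feasible, and local repeat tests are allowed. Interruption or discontinuation on judgment is available under 8.3.9.1 and 8.4.6.2, and urgent concerns go to the sponsor at once under 8.5.3. If one enzyme had a normal baseline, a literal reading of the first repeat-test trigger may bring in the 48–72 h repeat and close observation. All of this stands. A reader might infer that such a participant is left unmonitored until the next scheduled visit, four or eight weeks away; the documents do not support that.

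Third, keeping SAE reporting apart from evaluation is deliberate, and baseline multiples are sensible where entry allows ALT and AST up to 5× ULN. That is right for isolated enzyme rises. It is a weaker reason for leaving out cases that also have bilirubin > 2× ULN and no apparent cause.

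**Conclusion.** The gap is real and narrow. When ALT or AST is > 3× ULN but neither enzyme is > 2× Baseline, with none of the listed signs, symptoms or eosinophilia, a case can meet Appendix 8 while both stop scenarios fail. Four requirements are then missing: interruption, the competing-cause work-up, the 48–72 h liver profile with INR, and the bar on restart without an identified alternative cause.

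A reader might go further and infer that asymptomatic potential DILI in general has no stop rule. That is not so: scenario 1 needs no symptoms when the enzyme has doubled and bilirubin has doubled or INR has risen by > 0.2.

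The conclusion assumes that the enzyme above 3× ULN started above 1.5× ULN and that the investigator does not regard NASH as an apparent cause. Cases should be rare; the documents give no baseline distribution, so the number is unknown. The bilirubin gap is minor, since repeat testing, close observation and a stop if observation is not possible usually still apply. This is a cheap improvement to participant safety.

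**What to change.** In 8.5.3.1, change two scenarios to three and add: the participant meets the Appendix 8 potential-DILI definition. Attach the interruption, competing-cause work-up, 48–72 h liver profile with INR, medical monitor contact and restart condition that already follow scenarios 1 and 2. Leave the baseline multiples in scenario 1 unchanged. This covers both gaps.

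The cost is one sentence in an amendment or site clarification letter, with no new scheduled visits, and a few additional interruptions. Some may become permanent, because restart needs a definite alternative cause and a return to Baseline. A permanent stop before Week 20 has an efficacy cost too: under 8.5.1.1 the early-termination biopsy is then only something to consider, and a missing biopsy counts as nonresponse (Protocol 9.5.2.1, SAP 6.1.1). The new trigger still depends on the investigator's view of other apparent causes, so it narrows discretion without removing it.

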8.5.3.2 Overdose

An overdose is defined as the accidental or intentional administration of any dose of a product that is considered both excessive and medically important. All occurrences of overdose must be reported as SAEs (see [Appendix 8](#)).

In the event of an overdose, the investigator should do the following:

1. Contact the medical monitor immediately
2. Closely monitor the participant for AEs/SAEs and laboratory abnormalities for 14 days after the overdose
3. Obtain a plasma sample for PK analysis within 4 days from the date of the last dose of study medication if requested by the medical monitor (determined on a case-by-case basis)
4. Document the quantity of the excess dose as well as the duration of the overdosing in the eCRF

8.5.3.3 Physical Examinations

Physical examinations may be performed by a Doctor of Medicine (MD) or equivalent, or someone who is authorized to perform the examinations by training and has been delegated this task by the principal investigator.

Full examinations and abbreviated examinations will be performed as specified in the Schedule of Activities ([Section 1](#)).

A full examination will include general appearance, skin, head, eyes, ears, nose, throat, neck, thyroid, chest/lungs, heart, abdomen, lymph nodes, extremities, and body weight.

Abbreviated examinations will include an abdominal exam and symptom-focused assessments. An abbreviated examination may note any changes in the participant's condition (body systems) since the last assessment and does not preclude examination of any of the other body systems as clinically indicated. Every effort should be made to ensure the same

evaluator will complete the examination for each participant at all visits throughout the study. Documentation of who performed the examination is to be recorded in source notes.

8.5.3.4 Vital Signs

Schedules for vital sign collection are provided in [Section 1](#). Vital signs will include heart rate, respiratory rate, sitting SBP and DBP (to be taken after at least 5 minutes sitting at rest), and oral temperature.

8.5.3.5 Electrocardiograms

Twelve-lead ECGs should be collected at similar times during Baseline and on-treatment visits. ECGs may be collected at any time prior to study medication dosing or PK sample collection. ECGs should be recorded after the participant has been supine for at least 5 minutes. ECG parameters, including QTcF, will be collected on the eCRF.

If a participant has a QTcF > 480 msec during the Screening Period, it should be confirmed by repeat ECG 30-60 minutes after the initial ECG. If the QTcF is confirmed to be > 480 msec, the participant should not be allowed to participate in the study.

If a participant has a QTcF > 480 msec at an on-treatment visit, it should be confirmed by repeat ECG 30-60 minutes after the initial ECG. If the QTcF is confirmed to be > 480 msec, the medical monitor should be contacted.

8.5.3.6 Immunogenicity

Throughout the study, the potential for immunogenicity of BMS-986036 will be monitored as indicated in the Schedule of Activities (Section 1). In participants that experience immunogenicity, neutralizing activity and exposure-efficacy relationship will be assessed for evidence of a clinical impact on safety and efficacy.

Immunogenicity Assessment Methodology

Participants will be monitored for antibodies to BMS-986036 (drug) using an ADA homogenous bridge assay with electrochemical luminescence detection. Samples will first be screened for potential positive anti-BMS-986036 responses. Then, the samples with positive anti-BMS-986036 responses will be confirmed for specificity using an immunodepletion format with BMS-986036 and nonPEGylated drug. The reactivity of confirmed positive responses will be characterized as “BMS-986036” (specific to the FGF21 region) or “PEG” (specific to the PEGylated region) based on the immunodepletion specificity. Additionally, samples with confirmed positive responses will be titrated to determine the relative positive response.

Participants will also be monitored for antibodies to FGF21 using recombinant Met-FGF21 in a homogenous bridge assay with electrochemical luminescence detection. Samples will first be screened for potential positive anti-FGF21 responses. Then the samples with positive antiFGF21 responses will be confirmed for specificity using an immunodepletion format with wild-type sequence FGF21. Samples with confirmed positive anti-FGF21 responses will be titrated to determine the relative positive response.

Samples positive for anti-BMS-986036 antibodies or positive for anti-FGF21 antibodies will be tested for neutralizing activity in a functional cell based neutralizing antibody assay. The assay measures the ability of an anti-BMS-986036 or anti-FGF21 antibody to inhibit or block Erk1 activation that is induced when FGF21 or drug binds to the β -Klotho and FGF-Rs.

Long-Term Immunogenicity Follow-Up

All participants will have samples collected for immunogenicity at 6 months (\pm 14 days) after the Week 52/PTFU Visit. Samples collected from participants may not be analyzed if: 1) participant is not on active drug, 2) participant is negative for anti-drug and/or anti-FGF21 antibody titers at the Week 52/PTFU Visit, or 3) participant has evidence of stable or decreasing antibody titers for 2 visits prior to the 6-month posttreatment visit.

Participants with positive anti-drug and/or anti-FGF21 antibodies at the Week 52/PTFU Visit and without 2 consecutive stable or decreasing antibody titers will be followed for up to 14 months after the Week 52/PTFU Visit (1 month is defined as 4 calendar weeks) until antibody titers decrease for 2 consecutive visits (these additional visits will be conducted at approximately 9 months and 12 months after the Week 52/PTFU Visit). The sponsor or designee will inform the clinical site if a participant needs to return for immunogenicity follow up beyond 6 months. If, at 12 months after the Week 52/PTFU Visit, a participant has an increasing titer (compared to the previous titer), an additional follow-up visit will be performed at approximately 14 months (1 month is defined as 4 calendar weeks) after the Week 52/PTFU Visit; at this visit, anti-drug and anti-FGF21 antibodies, as well as additional laboratory assessments (basic metabolic panel, hemoglobin A1c [REDACTED]), will be collected.

Participants who discontinue from the study prior to the Week 48 Visit will be offered additional Long-Term Immunogenicity Follow-Up Visits, as above. For these participants, prior immunogenicity results will be used to determine whether the participant should be offered Long-Term Immunogenicity Follow-Up Visits beyond the 6-month posttreatment assessment. Additional Long-Term Immunogenicity Follow-Up Visits should occur approximately 9, 12, and 14 months, if applicable (1 month is defined as 4 calendar weeks) after their last study visit.

Refer to the decision tree in [Appendix 10](#) for more details regarding Long-Term Immunogenicity Follow-Up Visits.

